## **11. ETHICS**

### **11.1. Institutional Review Board (IRB)/Ethics Committee (EC)**

It is the responsibility of Cegecim to have prospective approval of the study protocol, protocol amendments, from an appropriate IRB/EC as necessary in the participating countries. All correspondence with the IRB/EC should be retained in the study File.

### **11.2. Ethical Conduct of the Study**

The study will be conducted in accordance with legal and regulatory requirements, as well as with scientific purpose, value and rigor and follow generally accepted research practices such as *Good Pharmacoepidemiology Practices* (GPP) issued by the International Society for Pharmacoepidemiology (ISPE), the International Society for Pharmacoeconomics and Outcomes Research (ISPOR) guidances, Pharmaceutical Research and Manufacturers Association (PhRMA) guidelines and similar.

### **11.3. Subject Information and Consent**

Not applicable.

## **12. COMMUNICATION AND PUBLICATION OF STUDY RESULTS**

### **12.1. Communication of results by Pfizer**

Pfizer fulfils its commitment to publicly disclose the results of studies through posting the results of this study on ClinicalStudyResults.org. Pfizer posts the results of studies that fall into either of the following categories:

- Studies that Pfizer registered on [www.clinicaltrials.gov](http://www.clinicaltrials.gov) regardless of the reason for registration; OR
- All other studies for which the results have scientific or medical importance as determined by Pfizer.

Results are posted in two formats:

- The results of studies applicable under the US Food and Drug Administration Amendments Act of 2007 (FDAAA) and/or An Act Regarding Advertising by Drug Manufacturers and Disclosure of Clinical Trials (state of Maine Reporting Requirements) are posted on [ClinicalTrials.gov](http://ClinicalTrials.gov) in a tabular format called Basic Results.
- The results of all required studies (even if not previously registered to [ClinicalTrials.gov](http://ClinicalTrials.gov)) and any voluntarily registered studies are posted on [ClinicalStudyResults.org](http://ClinicalStudyResults.org) in a format called a Pharmaceutical Research and Manufacturers of America (PhRMA) website synopsis (PWS), the format established by the ICH-E3 Clinical Study Report (CSR) Synopsis.

For studies involving a Pfizer product, the timing of the posting depends on whether the Pfizer product is approved for marketing in any country at the time the study is completed:

- For studies involving products already approved in any country and applicable under FDAAA and/or state of Maine, Pfizer posts results within one year of the primary outcome completion date (PCD). For all other studies that do not involve a Pfizer product, Pfizer posts results one year from last, subject last visit (LSLV);
- For studies involving products that are not yet approved in any country, Pfizer posts the results of already-completed studies within 30 days after US regulatory approval, or one year after the first ex-US regulatory approval of the product (if only submitted for approval ex-US);
- For studies involving products whose drug development is discontinued before approval, Pfizer posts the results within one year after such discontinuation.

Primary Completion Date is defined as the date that the final subject was examined or received an intervention for the purposes of final collection of data for the primary outcome, whether the clinical trial concluded according to the pre-specified protocol or was terminated.

Pfizer posts citations only for publications that are accessible in recognized (searchable) publication databases. Single-centre results publications for a multi-centre study are generally not posted because they may not accurately reflect the results of the study.

**STATISTICAL ANALYSIS PLAN (SAP)
FOR NON-INTERVENTIONAL STUDIES**

**Non-Interventional Study Protocol
B1781044**

**Cohort Study of Venous Thromboembolism and Other
Clinical Endpoints Among Osteoporotic Women
Prescribed Bazedoxifene, Bisphosphonates or
Raloxifene in Europe**

**Statistical Analysis Plan
(SAP)**

Version: 2.0

Authors: PPD [redacted], Pfizer Inc.
PPD [redacted], Medical Research Department,
Cegecim Strategic Data (CSD).

Date: 27-September-2016

PASS information

Title	Cohort Study of Venous Thromboembolism and Other Clinical Endpoints Among Osteoporotic Women Prescribed Bazedoxifene, Bisphosphonates or Raloxifene in Europe.
Protocol number	B1781044
Version identifier of the SAP	2.0
Date of last version of the SAP	27 September 2016
EU Post Authorisation Study (PAS) register number	ENCEPP/SDPP/5395
Active substance	Bazedoxifene
Medicinal product	CONBRIZA
Product reference	EMA/H/C/000913, EU/1/09/511/001-005
Procedure number	EMA/H/C/000913/ MEA 012
Marketing Authorisation Holder (MAH)	Pfizer Limited
Joint PASS	No
Research question and objectives	This observational cohort study is being conducted to characterize the risk of selected adverse events of interest among a patient population prescribed bazedoxifene, raloxifene, or a bisphosphonate in usual clinical care outside of a randomized clinical trial setting. The main study objective is to estimate and compare the incidence rates of venous thromboembolism and other clinical endpoints among women receiving bazedoxifene and women receiving either a bisphosphonate or

	
raloxifene for treatment of osteoporosis. The main objective of the interim analysis is to determine if, based on the incidence rate of the primary endpoint (venous thromboembolism (VTEs)) and the number of patients accrued in each treatment group, there will be sufficient accrual of data/events to continue the study as planned or if there will be a need to amend the protocol and/or extend the study duration in order to accrue the number of events and patients required to preserve the minimal detectable incidence rate ratios targeted in the protocol.

Countries of study
	
Spain, Italy

Authors
	
PPD [redacted], ScD PPD [redacted] Epidemiology
 
Pfizer Inc [name]
 
Tel: PPD [redacted] Fax: PPD [redacted] Email: PPD [redacted]
 
PPD [redacted], PhD Statistician Medical Research Department, Cegedim Strategic Data (CSD)

TABLE OF CONTENTS

1 AMENDMENTS FROM PREVIOUS VERSION(S)

Version	Date	Summary of Changes/Comments
Version 1.0	18-November-2013	Not Applicable
Version 2.0	27-September-2016	Administrative changes. Updated SAP format to reflect CT24-GSOP-SD-GL04 Non-interventional (NI) Study Statistical Analysis Plan Template Version 1.0, Date 31-Dec-2013.

2 INTRODUCTION

Note: in this document any text taken directly from the protocol is *italicised*.

Osteoporosis is characterised by a decrease in bone mass and architectural deterioration of bone tissue. Subtle modifications of bone remodelling, related to abnormalities of bone turnover, can induce a substantial loss of bone over a prolonged period of time. A period of asymptomatic bone loss results in reduced bone strength. When bone loss is sufficient to cause mechanical weakness, fractures may occur spontaneously or as a result of minimal trauma. Osteoporotic fractures cause a substantial clinical and economic burden for society. Age and menopause are the two main determinants of osteoporosis. The cessation of ovarian production of estrogen, at the time of the menopause, results in an accelerated rate of bone loss in women.

Bazedoxifene (BZA) is a third generation non-steroidal selective estrogen receptor modulator (SERM) currently approved in the European Union (EU) for the treatment of postmenopausal osteoporosis in women at increased risk of fracture. BZA is an estrogen receptor ligand that exhibits tissue specific activity: BZA functions as an agonist in the bone and an antagonist in the breast and uterine endometrium. BZA was developed in tablet form and current dosing consists of once daily administration of a 20 mg tablet. BZA (Conbriza) was approved in Europe via the centralized authorization procedure in April 2009. The first EU launch occurred in Spain in September 2010 which was followed by launch in Italy in April 2011.

Currently, one other SERM, raloxifene (Evista®) is marketed in Europe for the treatment and prevention of postmenopausal osteoporosis.

Bisphosphonates are non-hormone compounds that bind to the bone surface and are then taken up by osteoclasts. Bisphosphonates have a profound effect on bone remodeling, and are widely used for the prevention and treatment of osteoporosis.

In clinical trials, BZA-treated women had an increased risk of venous thromboembolic events (VTEs) compared to placebo. VTEs are included in the product label as an important identified risk.

2.1 STUDY DESIGN

This Post Authorization Safety Study (PASS) is an observational, non-interventional epidemiologic cohort study using extracted data from proprietary longitudinal patient databases (LPD) in Italy and Spain. This study is being conducted to further characterize selected adverse events of interest among a patient population prescribed BZA, raloxifene, or a bisphosphonate in usual clinical care outside of a randomized clinical trial setting. This PASS is a post-authorization commitment to the Committee for Medicinal Products for Human Use/ European Medicines Agency (CHMP/EMA).

The LPD databases of Italy and Spain contain all drug prescriptions, diagnoses, demographic data, medical history (event data, risk factors) and other types of data electronically collected by participating general practitioners. The eligible population will be constructed from these anonymised LPD databases.

The total study period is planned for 8 years. This study was launched after BZA became commercially available in the participating countries, Italy and Spain. The subject inclusion/accrual period (also referred to as enrolment period) in the database began at the time of commercial launch of BZA in each country (September 2010 in Spain and April 2011 in Italy) and continued for approximately three years from the start of the study, Table 1. The index date for each patient was the date of the first recorded prescription for BZA or raloxifene or bisphosphonates during the enrolment period. Each woman must have at least 6 months of data prior to index prescription date to be included in the analysis, the baseline period. The study therefore consisted of three distinct periods:

- Pre-enrolment period: 6 months before launch day in a country
- Enrolment period: Approximately 3 years from launch day in a country.
- Follow-up period: 5 years of follow-up per patient from the index date.

Table 1: Study timelines by country

	Pre-enrolment Period 6 Months	Enrolment Period 3 Years*	Follow-Up Period 5 Years
Spain	April 1 st 2010- September 30 th 2010	October 1 st 2010- April 30 th 2014	May 1 st 2014- April 30 th 2019
Italy	November 1 st 2010- April 30 th 2011	May 1 st 2011- April 30 th 2014	May 1 st 2014- April 30 th 2019

* Due to low enrolment/accrual into the study, the original end of the study accrual period was extended from September 30th 2012 in Spain, and April 30th 2013 in Italy, to April 30th 2014 for both Spain and Italy. Extending the accrual period to April 2014 extended the study timelines by 1 year. The new accrual period for Spain is 43 months (October 1st 2010-April 30th 2014) and the new accrual period for Italy is 36 months (May 1st 2011-April 30th 2014).

Patients will be counted in according to the inclusion criteria.

Follow up for each endpoint will be from the index date to whichever of the following occurs first.

1. Endpoint under investigation
2. Last patient visit or completion of 5 years follow up, whichever occurs first.

Each patient will be followed for identification of selected endpoints for a period of up to five years from their index prescription date for BZA, bisphosphonate or raloxifene. The follow up will continue even if the woman discontinues the index medication or switches to a different medication during this five year follow up period. The follow up duration of an individual patient may be shorter than five years if the woman transfers out of the GP office that wrote the index prescription or if she dies.¹ In these situations the data will be censored on the date of last visit. This study will use the Cegedim Longitudinal Patient Database (LPD), an electronic medical records database. However, the Spanish and Italian databases of Cegedim Strategic Data (CSD) do not have recorded events of death and date of death. The discontinued patient's record indicate loss to follow-up for various reasons, such as patients' moving from the areas, patient's change of GPs or other various reasons. The number of patients who are lost to follow-up will be provided. A minimum of a six month history in the LPD database prior to the index date (at least one GP visit, whatever the motive of the visit to GP) is required for inclusion of population, in order to ensure a certain quality of information.

Study Population

The study population will be selected based on the following inclusion criteria and all eligible patients enrolled in this study will be included. No exclusion criteria were applied.

Any patient with a prescription for BZA (exposed cohort), raloxifene (comparator cohort) and bisphosphonate (comparator cohort) treatment accompanied with diagnosis of osteoporosis will be eligible when they meet other inclusion criteria. The detailed inclusion criteria will be as follows:

1. *Female*
2. *At least one prescription for BZA, raloxifene, or any bisphosphonate during the study inclusion period*
3. *A recorded diagnosis code of osteoporosis on or within 60 days prior to the index prescription date.*
4. *Age of patients ≥ 45 at the index prescription date*
5. *At least 6 months of follow-up data in the electronic medical record system prior to the date of index prescription.*

¹ The event of death and date of death are not recorded in CSD Italian and Spanish database. The discontinued patient's records indicate loss to follow-up for various reasons.

The applicability of the third criterion will be evaluated through performing a sensitivity analysis comparing those with osteoporosis diagnosis within 60 days and those without diagnosis within 60 days. This has become necessary due to a significant number of patients (> 45%) missing a recorded diagnosis of osteoporosis. If the venous thromboembolism rates of the two groups are comparable (i.e., difference within 20%), this criterion will not be included.

Data Source

This study will use the Cegedim Longitudinal Patient Database (LPD), an electronic medical records database that collects clinical data from primary care physician practices in the following European countries i.e., Spain, Italy, Germany, France, Belgium and UK. (In the UK the database is known as The Health Improvement Network (THIN).) For this study the Cegedim LPD in Italy and Spain will be used.

The Cegedim LPD obtains medical information from proprietary practice management software used during physician office visits to capture clinical data in an electronic medical record system. Physicians use the practice management software developed by Cegedim to maintain electronic medical records of their patients. In each country a panel of physicians using this electronic system volunteered to make available anonymized patient-level information from their practices for clinical research purposes. Since these data are being collected in usual clinical care in a non-interventional way, they reflect routine clinical practice in these countries. The panel of contributing physicians is maintained as a representative sample of the primary care physician population in each country according to age, sex, and geographical distribution. Additionally in most countries (including Spain and Italy), the patient population is representative of the respective country population according to age and sex distribution, as provided by national statistic authorities.

Table 2: Doctor and patient populations in the Cegedim LPD by country

	Italy	Spain
Number of physicians in the panel	700	300
Average number of patients who consulted GP at least once in a year	800,000	320,000

The patient data in the LPD form a nationally representative sample. Data have been collected in Italy since 2004 and in Spain since 2006, providing several years of medical history, including comorbidity and concomitant medication use information. Of the patients included in the Spanish and Italian LPD, there are currently approximately 68,000 women with drug-treated osteoporosis. Between 1 and 6% of these patients are taking raloxifene, depending on the region; most of the rest are prescribed a bisphosphonate (Cegedim, data on file).

Data are entered regularly during usual patient care, submitted daily to the Cegedim coordinating center, cleaned and de-identified, and then made available for research.

Anonymized patient data collected from each GP practice includes:

- *Demographic information (age, gender)*
- *Medical history (event dates, diagnoses, risk factors, referrals to specialists)*
- *Therapeutic history (date/length of prescription, molecule/product, dosage)*
- *Additional information (test results, immunizations, height, weight, blood pressure)*

Patient data collected by Cegedim in each country participating in the LPD varies to some extent to accommodate local needs. However, all countries collect data on medical comorbidities and outcomes, prescriptions, demographics, and physician characteristics.

In the Cegedim electronic medical record system diagnosis of clinical events are recorded as diagnostic codes. These codes from the different participating countries will be harmonized based on pre-specified algorithms developed prior to the analysis and listed in the statistical analytic plan.

Cegedim LPD does not collect hospitalization data directly in Italy and Spain. Information on hospitalizations is captured in the patient's general practice file during follow-up visits with the patient's general practice physician following discharge from the hospital. However, this information is not systematically collected and there is no established linkage between the medical records at the general practices and at the hospitals.

Table 2: Data coding conventions in the different countries

	Italy	Spain
Drug code dictionary	Farmadati	Vademecum
Therapy classification	Anatomical Therapeutic Chemical (ATC)	ATC
Disease classification	ICD-9	Code ICPC mapped to ICD-9

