5.4 SUBGROUPS

Age stratified randomly selected subgroup

In the current dataset, there are 1,823 patients in the bazedoxifene group and 82,041 patients in the bisphosphonate group. This means that there is more than 40 times the number of subjects in the bisphosphonate group compared to the number of subjects in the bazedoxifene group. To limit the number of patients in the bisphosphonate group, an age stratified random subgroup will be selected. Based on the sample size and relative risk estimates provided in the final study protocol (study protocol section 7.1, Sample size calculation), the 1,823 bazedoxifene subjects will be adequately matched by a ratio of 1:6 bisphosphonate subjects. Therefore $1,823 \times 6 = 10,938$ bisphosphonate treated subjects are needed to be randomly selected from the total of 82,041 bisphosphonate treated subjects.

Selection scheme: The age of subjects in the study will be categorized into 4 groups (45-49, 50-59, 60-69, and ≥ 70). In the bisphosphonate group, the percentage of subjects in each of these age groups is 1.4%, 13.7%, 28.7%, and 56.2% respectively. To maintain the same proportion of subjects in each age group for the bisphosphonate subgroup, there will be $1.4\% \times 10,938 = 153$ bisphosphonate treated subjects randomly selected from the 45-49 age group; $13.7\% \times 10,938 = 1,499$ subjects randomly selected from the 50-59 age group; $28.7\% \times 10,938 = 3,139$ subjects randomly selected from the 60-69 age group; $56.2\% \times 10,938 = 6,147$ subjects randomly selected from ≥ 70 age group.

Incident cases of study endpoints

Women with a history of study end points recorded prior to the index prescription will not be included in the analysis for that specific outcome, but will be analyzed separately as subgroups for each study end point. The analyses of the primary and secondary endpoints will be performed using these incident cases of study endpoints subgroups.

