In this study the proportion and demographic and clinical characteristics of patients that switch medications between the study drugs will be reported alongside patients that do not switch medications. Both the AT and CR analytic approaches will be used for all study endpoints and the results reported. In the CR method, if a patient switches from one exposure (study drug) cohort group to another, they will have several treatment durations and will belong to multiple cohort groups but will be analyzed according to their original exposure cohort group (i.e., CR/intent to treat approach). In the AT approach, all exposure cohort groups will be included as a time-dependent variable. With the exposure cohort group as a time-dependent variable, each event will be assigned to the treatment being taken at the time of occurrence. The duration of treatment for each cohort group will be from the date of the first prescription to the date of the event or to the end of treatment, whichever occurs first. The covariates of patients that switched treatment at the time of the event or at the end of follow-up would be considered in this model.

[figure not shown]
The following diagrams shows some example of calculating duration for patients with switched treatments with both the AT and CR approaches.

Figure 2a. Calculating the duration of treatment for patients that switched treatment using the as-treated (AT) approach.

A, B, C: Treatment cohort types. X= Incidence date of primary end point

Figure 2b. Calculating the duration of treatment for patients that switched treatments using the cumulative risk (CR) approach.

A, B, C: Treatment cohort types. X= Incidence date of primary end point

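### If cohorts follow the index drug, the 13.3% bisphosphonate sample drops about 87% of bisphosphonate-to-bazedoxifene switchers from the as-treated analysis of population (a), with no weighting

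*SAP*

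**What the plan says.** **Index date.** SAP 2.1: "The index date for each patient was the date of the first recorded prescription for BZA or raloxifene or bisphosphonates during the enrolment period". SAP 5.4 repeats this rule for the new-user subgroup.

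**Eligibility.** SAP 2.1, Study Population, admits "Any patient with a prescription for BZA (exposed cohort), raloxifene (comparator cohort) and bisphosphonate (comparator cohort) treatment" accompanied by an osteoporosis diagnosis, subject to the other criteria.

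**Switchers.** SAP 8.1.4 plans two analyses for all endpoints. In the cumulative-risk analysis, switchers "will belong to multiple cohort groups but will be analyzed according to their original exposure cohort group". In the as-treated analysis exposure is time-dependent, and "each event will be assigned to the treatment being taken at the time of occurrence".

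**Sampling.** SAP 5.4 reports that "there are 1,823 patients in the bazedoxifene group and 82,041 patients in the bisphosphonate group". At a 1:6 ratio, 10,938 "bisphosphonate treated subjects are needed to be randomly selected from the total of 82,041 bisphosphonate treated subjects", in four age strata. SAP 8.2.5 makes this population (a): all BZA women, all raloxifene women and the bisphosphonate sample. Population (b) is the new-user subgroup, for which no sampling is stated.

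**Protocol.** Section 4 says that all women who meet the inclusion criteria are analysed, with no sampling. SAP 5.1 defines the full analysis set in the same spirit.

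**The concern.** BZA was launched into a population in which most drug-treated women took a bisphosphonate (SAP 2.1, Data Source). A woman who fills a bisphosphonate prescription after launch and later moves to BZA has a bisphosphonate index date. The as-treated analysis is the one that should credit her later time to BZA, but it can do so only if she is in the dataset. The sample is drawn by age alone. No rule retains women who later receive BZA, and no sampling weight is specified.

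Two things are at stake. The first is precision: BZA exposure is the limiting resource, and SAP 2.1 says accrual was extended because enrolment was low. The second is the make-up of the as-treated BZA time. BZA-first women enter at 100% and bisphosphonate-to-BZA women at 13.3%, unweighted. SAP 8.1.4 says that treatment changes often follow treatment failure or side effects, so the two kinds of women may differ in risk of venous thromboembolism (VTE). The as-treated hazard ratio would then depend partly on a sampling fraction chosen for convenience.

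**Working it through.** **1. The plan's own figure.** 1,823 × 6 = 10,938, and the strata add up: 153 + 1,499 + 3,139 + 6,147 = 10,938. Both reproduce.

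**2. Sampling fraction.** 10,938 / 82,041 = 13.3%, so 86.7% are left out. Allocation is proportional to age group, so the fraction is the same in every stratum. The inverse weight is 82,041 / 10,938 = 7.5.

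**3. Consequence under each reading.**
- Groups counted by index drug: bisphosphonate-to-BZA switchers sit among the 82,041, and on average 86.7% of them and of their BZA time are lost.
- Groups counted by ever-use of BZA: switchers sit among the 1,823, all of whom are kept, and the loss is nil.

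**4. Number of switchers.** The documents give none. Assume that a share s of ever-BZA women was first seen on a bisphosphonate. Switchers = 1,823 × s / (1 − s); kept = 13.3% of them.

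| s (assumed) | Switchers | As % of 82,041 | Kept | Dropped |
|---|---|---|---|---|
| 10% | 203 | 0.25% | 27 | 176 |
| 25% | 608 | 0.74% | 81 | 527 |
| 50% | 1,823 | 2.2% | 243 | 1,580 |

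The number dropped equals the whole BZA group when 1,823 / (82,041 × 0.867) = 2.6% of bisphosphonate women switch.

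**5. Precision.** Inputs: VTE rate 1.74/1000 person-years (PY) without a SERM (Protocol 7.1); rate ratio 2; 3.5 PY per woman (assumed, close to five years with 15% annual loss); half of a switcher's follow-up, 1.75 PY, on BZA (assumed). Wald interval: 2 × exp(±1.96 × SE), with SE = √(1/E₁ + 1/E₀), where E₁ and E₀ are expected events on BZA and on bisphosphonate.

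- BZA PY = 1,823 × 3.5 + 1.75 × (switchers in the dataset) = 6,380.5 + 1.75 × n.
- Bisphosphonate PY = 10,938 × 3.5 − 1.75 × (sampled switchers), held fixed in the comparison.
- Example, s = 50%, sampled: BZA PY = 6,380.5 + 1.75 × 243 = 6,806, E₁ = 6,806 × 0.00174 × 2 = 23.7. Bisphosphonate PY = 38,283 − 425 = 37,858, E₀ = 65.9. SE = 0.240, CI 1.25-3.20.
- Same s, all switchers kept: BZA PY = 6,380.5 + 1.75 × 1,823 = 9,571, E₁ = 33.3, SE = 0.213, CI 1.32-3.03.

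| s | BZA PY, sampled | 95% CI, sampled | BZA PY, all kept | 95% CI, all kept |
|---|---|---|---|---|
| 10% | 6,428 | 1.24-3.23 | 6,735 | 1.25-3.20 |
| 25% | 6,522 | 1.24-3.22 | 7,444 | 1.27-3.15 |
| 50% | 6,806 | 1.25-3.20 | 9,571 | 1.32-3.03 |

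With 4.25 PY per woman, which reproduces 10 of the 12 intervals in Protocol Table 3, and 1% of the 82,041 switching (820 women), the CI moves from 1.30-3.08 to 1.33-3.00. At 5% (4,102 women) it moves from 1.32-3.03 to 1.42-2.81.

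**6. Mix of BZA time.** Switchers' share of as-treated BZA time at s = 50% is 425 / 6,806 = 6.2% when sampled and 3,190 / 9,571 = 33.3% when all are kept. At s = 10% it is 47 / 6,428 = 0.7% against 355 / 6,735 = 5.3%.

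**The case against.** **Index-drug counting is inferred.** SAP 2.1 defines an index date and never says that 1,823 and 82,041 were counted by index drug. SAP 8.1.4 says of switchers that "they will have several treatment durations and will belong to multiple cohort groups". This stands: if the counts are by ever-use, nothing is lost. The index-drug reading remains the more natural one, because an original cohort needs a single starting drug.

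**The eligibility sentence does not settle it.** A reader might infer that SAP 2.1 contradicts itself by placing every BZA recipient in the exposed cohort. That sentence concerns who is eligible; its bracketed labels name the drug groups and do not allocate switchers.

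**Cumulative risk.** A reader might infer that switchers are simply miscounted as bisphosphonate users. That happens only in the cumulative-risk analysis, where SAP 8.1.4 discloses the misclassification and pairs it with the as-treated analysis. The dilution is also small: with 5% switching, half the time on BZA and a rate ratio of 2, the comparator rate rises by 0.05 × 0.5 × (2 − 1) = 2.5%.

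**Scope.** The loss is confined to population (a). Population (b) has no stated sampling, and SAP 8.1.4 uses newly prescribed patients first for time to event. A refill also qualifies as an index prescription only with an osteoporosis code in the preceding 60 days, unless that criterion is dropped, which limits the number of switchers.

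**Bias.** A reader might infer that the sampling biases the comparison. It is random within age and does not depend on outcome, so its demonstrable cost is precision. The changed mix matters only if VTE risk differs between BZA-first women and switchers, which the documents do not quantify.

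**Conclusion.** The point holds conditionally. If the SAP 5.4 groups are index-drug counts, the as-treated analysis of population (a) loses about 86.7% of bisphosphonate-to-BZA switchers and their BZA time, while BZA-first women are kept in full and unweighted. The sampling also conflicts with Protocol section 4 on either reading.

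The proportion follows from the SAP's own numbers; the absolute loss does not. For an assumed s of 10% to 50%, 176 to 1,580 women are dropped. The gain in the lower confidence limit at a rate ratio of 2 runs from about 0.01 to 0.07. Every interval excludes 1 with or without the change, so this improves precision and interpretability and does not rescue a failing comparison. The calculation treats every switcher as bisphosphonate-first; any who came from raloxifene are not sampled out, and the loss would be smaller.

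The documents do not support moving the BZA index date to the first BZA prescription as a clear correction. That would apply the 60-day diagnosis criterion at a new date and bring previously treated women into the BZA cohort. Ending comparator time at the switch would be the kind of censoring that SAP 8.1.4 warns can bias.

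**What to change.** 1. In SAP 5.4, state whether 1,823 and 82,041 are counts by index drug or by ever-use.
2. Before sampling, report the number of bisphosphonate-to-BZA switchers and their BZA person-years.
3. Run the as-treated analysis on all 82,041 bisphosphonate women, which also meets Protocol section 4. Alternatively, keep every woman who ever receives BZA at weight 1, and give sampled bisphosphonate women who never receive it the inverse-sampling weight (about 7.5). If sampling is kept, reconcile it with Protocol section 4.
4. Leave the index-date rule and the cumulative-risk analysis as they are.

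The cost is SAP wording plus either a larger analysis file or a weighted Cox model with robust variance. No new data are needed.
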